7.6 Subject population

All eligible subjects will be included in the analysis population (full population analysis).

7.7 Procedure(s) to account for missing or spurious data

Multiple imputation using Chained Equations approach (MICE) will be used to fill in missing data. Ten imputations (M=10) will be chosen to obtain valid inference and reduce sampling variability resulting from the imputation process. Variables with a missing rate above 20% will be excluded and the outcomes will be included in the imputation model. All 10 datasets will be analyzed and combined using Rubin rules. A complete case analysis will also be performed as a sensitivity analysis to assess the robustness of the results.

8 Consent

Due to the nature of this data collection study, consent will not be sought.

In order to maintain confidentiality, the participant will be identified only by subject number. Participant data will be collected from electronic health records by appropriately trained and authorised member(s) of the study team who must be identified and authorised in writing by the Principal Investigator (PI). A delegation of responsibility log will be updated accordingly.

As data collection is entirely retrospective, participants will not need to attend any additional visits. Participants will not have undergone any procedures above their routine standard of care.

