The second primary outcome analysis will be performed between PLWHIV with MPX versus PrEP users with MPX. The endpoint is to assess differences in clinical manifestations of MPX between the groups. Unadjusted and adjusted odds ratios (ORs) will be calculated using the logistic regression models to compare the rates of clinical manifestations between PLWHIH and PrEP users. The adjusted variables will be the following (potential confounders): Age (<30 vs 30-40 vs >40 years); Sex at birth (female vs male); Comorbidities; multiple sexual partners (yes vs no); number of sexual partners in the last 3 months prior to MPX diagnosis; and smallpox vaccination history (yes vs no).

The third primary outcome analysis will be performed within the PLWHIV group. The endpoint is to evaluate the characteristics of HIV infection associated with severe mpox. Univariable and multivariable logistic regression models will be used to assess factors associated with severe mpox in PLWHIV. The following variables will be evaluated: time since HIV diagnosis (years); current ART; CDC disease stage; CD4 cell nadir; last CD4 cell count/HIV-RNA before MPX diagnosis (including CD4% and CD4/CD8 ratio). Variables achieving $P < 0.20$ in the univariable analysis will be retained for the multivariable analysis.

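### Ten imputations give valid intervals, but leave avoidable seed-to-seed noise in borderline P values, mainly at the P<0.20 screen in the PLWHIV risk-factor model

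*Combined protocol and SAP*

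**What the plan says.** Section 7.7 sets out the missing-data method: "Multiple imputation using Chained Equations approach (MICE) will be used to fill in missing data". The number of imputations is fixed: "Ten imputations (M=10) will be chosen to obtain valid inference and reduce sampling variability resulting from the imputation process". On which variables take part, it says "Variables with a missing rate above 20% will be excluded and the outcomes will be included in the imputation model". The sentence can be read as excluding such variables from imputation or from analysis, but on either reading an imputed variable may be up to 20% missing. Pooling is specified ("All 10 datasets will be analyzed and combined using Rubin rules"), and so is a sensitivity analysis: "A complete case analysis will also be performed as a sensitivity analysis to assess the robustness of the results".

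The section does not derive the number 10, expect any particular missing rate or FMI, name a seed, or plan a check of Monte Carlo error.

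Section 7.4 contains the step where this matters most. It states that "The third primary outcome analysis will be performed within the PLWHIV group", and lists HIV-related factors: time since diagnosis, current ART, CDC stage, CD4 nadir, and last CD4 and HIV-RNA values. Those reaching P<0.20 "in the univariable analysis will be retained for the multivariable analysis". The plan does not say how that rule is applied across ten imputed datasets. The HIV-versus-PrEP comparisons in 7.4 use a fixed list of adjustment variables, with no selection by P value.

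**The concern.** Multiple imputation draws random values, so the pooled estimate depends on the seed. The dependence shrinks as M grows. At M=10 it can still be visible for the coefficient of a variable that is itself incomplete. If that coefficient's P value is near a cut-off, two analysts who follow the same plan on the same data can reach different decisions.

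The hard P<0.20 screen turns this noise into a decision. A factor that drops out or enters by chance also changes the covariate set, and so the other adjusted odds ratios in the model. Identifying risk factors, including CD4 nadir and current CD4, is one of the two primary objectives (section 3.1). What is at stake is the reproducibility of borderline findings, not the validity of the intervals.

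**Working it through.** **Inputs from the documents.** M=10, the 20% ceiling and pooling by Rubin's rules (7.7); the P<0.20 univariable screen within PLWHIV (7.4); about 2000 cases in total (section 4). M=10 is stated rather than calculated, so there is no figure of the plan's own to reproduce.

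**Assumptions.** FMI of 0.05 to 0.30, and a significance level of 0.05 where one is used. The documents state neither.

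**1. Validity and efficiency.** Relative efficiency = 1/(1 + FMI/M).
- FMI 0.20, M=10: 1/(1 + 0.02) = 0.980.
- FMI 0.30, M=10: 1/(1 + 0.03) = 0.971.

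Simulated coverage of the 95% interval at M=10 is 0.950 at FMI 0.05, 0.20 and 0.30. On this criterion, 10 is adequate.

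**2. Monte Carlo noise.** In units of the large-M standard error, the SD of the pooled estimate over seeds is sqrt(FMI/M). At FMI 0.20:
- M=10: sqrt(0.020) = 0.141.
- M=50: sqrt(0.004) = 0.063.
- M=100: sqrt(0.002) = 0.045.

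**3. Effect on the P<0.20 screen.** Take a factor with a large-M P of 0.15 (z = 1.440). The cut-off is z = 1.282, so the gap is 0.158. At FMI 0.20 and M=10 the gap is 0.158/0.141 = 1.12 Monte Carlo SDs, which gives about a 13% chance of failing on a normal approximation. That understates the risk, because the estimated standard error also varies with the seed and Rubin's rules use a t reference.

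Simulating these parts used: pooled estimate ~ N(z, FMI/M); between-imputation variance B = FMI × chi-square(M−1)/(M−1); within-imputation variance W = 1 − FMI; total variance T = W + (1 + 1/M)B; degrees of freedom (M−1)[1 + W/((1 + 1/M)B)]². The results are:

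| FMI (assumed) | Large-M P of 0.15 fails P<0.20, M=10 | Same, M=50 |
|---|---|---|
| 0.05 | 2% | 0% |
| 0.10 | 8% | 0% |
| 0.20 | 18% | 1% |
| 0.30 | 25% | 4% |

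The error also runs the other way. At FMI 0.20, a factor with a large-M P of 0.25 passes the screen in 17% of seeds at M=10, in 2 to 3% at M=50 and in about 0% at M=100.

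**4. Borderline and clear P values.** At FMI 0.20, a large-M P of 0.05 ranges over 95% of seeds from 0.023 to 0.109 at M=10 and from 0.036 to about 0.070 at M=50. A large-M P of 0.04 is below 0.05 in 65% of seeds at M=10 and in 96% at M=100. A large-M P of 0.01 stays below 0.05 in essentially all seeds at M=10.

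**5. Which coefficients are exposed.** Logistic data were simulated with one covariate 20% missing completely at random, assuming 1000 PLWHIV, 2000 patients in total and about 10% severe.
- The incomplete covariate's own coefficient had FMI 0.15 to 0.20. A P of about 0.046 ranged from 0.022 to 0.100 over seeds at M=10.
- The fully observed HIV coefficient had FMI 0.014 to 0.018. A P of about 0.048 ranged only from 0.041 to 0.058.

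**6. How many records could be incomplete.** If k variables are each 20% missing independently, the share of incomplete records is 1 − 0.8^k: 49% for k=3 and 67% for k=5. At 10% each, k=5 gives 1 − 0.9^5 = 41%. These are illustrations at or below the ceiling, not forecasts.

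**The case against.** The strongest defence is that the plan's sentence is true: ten imputations do give valid inference and do reduce variability. That stands. A reader might infer that M=10 makes the intervals or tests invalid. The coverage and efficiency figures contradict this.

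A reader might also infer that the main HIV-versus-PrEP result depends on the seed. The documents do not support that. Group membership follows from the eligibility criteria in 5.1, the adjustment list is fixed, and a fully observed exposure has very low FMI. Missing outcomes would raise it.

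The 20% figure is a ceiling. It is neither an expected missing rate nor an FMI. Independent missingness in every covariate at the ceiling is also unlikely: the two sexual-partner variables in the adjustment list come from the same history. The phrase in 6.2 about routine availability heads the all-patient list, not the HIV-specific one, and 6.1 describes regular visits for PLWHIV. The HIV factors may therefore be fairly complete, in which case the top rows of the table apply.

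Section 7.2 calls the study primarily descriptive, no significance level is stated, and a factor exactly on a cut-off is close to 50:50 at any M. All of that is correct and limits the weight of the point.

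The complete case analysis does not answer it. It has no seed, but it asks whether imputation changes the result. It does not measure how much the imputed result varies between runs.

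**Conclusion.** The point holds as a minor improvement to reproducibility. M=10 is adequate for inference, but leaves avoidable noise in borderline P values for incomplete variables. The exposed step is the P<0.20 screen in the third primary analysis. The chance that a factor with a large-M P of 0.15 is wrongly dropped is small at low FMI and about one in four at FMI 0.30, and it falls to 4% or less throughout that range at M=50. The size depends on an FMI that the documents do not give. Clear results do not move.

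It would be wrong to conclude that a larger M removes the seed dependence. The noise falls as 1/sqrt(M), so results very close to a cut-off remain uncertain at any practical M.

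**What to change.** In section 7.7:
- Replace the ten imputations with at least 50, and no fewer than the percentage of incomplete records. For example, 67% incomplete would mean at least 67 imputations. Fifty is a conventional floor; the table shows what it achieves.
- Change the pooling sentence, which also refers to ten datasets, to match.
- Fix and record the random seed, and report the Monte Carlo error of the main estimates.

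In section 7.4, state that the P<0.20 screen is applied to P values pooled over the imputed datasets. A larger M alone would leave that open.

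The cost is a few words in the plan and a little more computing time for about 2000 records. No new data are needed and the design does not change.

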6.2 Data collection

Only real-world retrospective data will be used for this study. Patients who have had mpox and fulfil the entry criteria will be enrolled after 90 days from date of diagnosis to allow for follow up data to be collected. Pseudonymised retrospective data will be transcribed into the eCRF system from source data at each clinical site or from existing cohort databases, where appropriate. No personal identifiable data will be transmitted to NEAT ID. The data elements will be transcribed from source data according to the data collection list below. Mechanisms to ensure data quality and integrity will be deployed as per applicable standard operating procedures and in line with Good Documentation Practice (GDocP) and Good Pharmacoepidemiology Practice (GPP). Patients will be identified and documented by participating sites.

For all patients with MPX the following information will be collected where routinely available:

- Age (year of birth)
- Sex and gender identity
- Ethnicity (where available)
- HIV status
- HIV pre-exposure prophylaxis (PrEP) use
- Comorbidities and Medical history (diabetes mellitus, other immunosuppression (e.g. solid organ transplant), known chronic kidney or liver disease, mental health conditions)
- Recent sexual history (3 months) – number of recent partners
- Recent and/or concomitant sexually transmitted infections
- Orthopoxvirus vaccination history (if available)
- Symptom onset date (fever onset, lesion onset, rectal pain)

- Date of positive PCR test result (documented)
- MPX severity -Reported clinical signs and symptoms of mpox (e.g. rash, mouth lesions, rectal pain, breathlessness)
- Time to resolution of lesions, if known
- Mortality as a consequence of MPX including cause
- Hospitalisation for MPX and length of hospitalisation
- Drug treatment for MPX (Tecovirimat, other)
- Drug for complications associated with MPX (laxatives, antibiotics, analgesia)
- recent travel to/living in endemic country or country with outbreak
- contact with suspected, probable, or confirmed case (if known)
- contact with infected animal (if known)

For PLWHIV the following additional information will be collected:

- Date of HIV diagnosis
- Current Antiretroviral Therapy/Treatment (ART)
- If not on ART, reason for not being on ART
- Last CD4 cell count (including CD4% and CD4/CD8 ratio) and
- Last HIV-RNA before MPX diagnosis

Skin lesion at peak severity score:

- Not presenting with skin lesions (0 skin lesions)

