7.4 Primary outcome analysis

The first primary outcome analysis will be to describe outcomes of MPX in PLWHIV and in PrEP users in terms of severity of lesions, time to lesion resolution, hospitalization, death.

The rate of serious lesions will be estimated by dividing the number of participants with serious lesions by the total number of participants in the full analysis population. Unadjusted and adjusted odds ratios (ORs) will be calculated using the logistic regression model to assess the impact of HIV on the occurrence of serious lesions compared to PrEP users.

Because some participants' lesion may not be healed by the end of the study period and, therefore, the duration of resolution would not be known, and thus right-censored, survival analysis methods such as the Kaplan-Meier and Cox model will be used to assess the time to lesion resolution. Kaplan-Meier estimates will be used to estimate the median time to lesion resolution. Unadjusted and adjusted hazard ratios (HR) will be estimated using the Cox proportional hazard model to assess the impact of HIV-infection on the time to lesion resolution compared with PrEP users.

The hospitalization rate will be estimated by dividing the number of participants hospitalized for mpox infection by the total number of participants in the total analysis population. Unadjusted and adjusted odds ratios (ORs) will be calculated using the logistic regression model to compare hospitalization rates between PLWHIV and PrEP users.

The mortality rate will be estimated using the Kaplan-Meier Method. Unadjusted and adjusted hazard ratios (HR) will be calculated using the Cox proportional hazard model to compare the rates of mortality between PLWHIV and PrEP users.

Adjustment variables will include the following potential confounders: Age (<30 vs 30-40 vs >40 years); Sex at birth (female vs male); Comorbidities; multiple sexual partners (yes vs no); number of sexual partners in the last 3 months prior to mpox diagnosis; and smallpox vaccination history (yes vs no).

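### The 20% missing-data rule in Section 7.7 could drop a prespecified confounder or HIV exposure on missingness alone, and it conflicts with the fixed adjustment sets in 7.4 and 7.5

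*Combined protocol and SAP*

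**What the plan says.** Section 7.7 plans multiple imputation for missing data: "Multiple imputation using Chained Equations approach (MICE) will be used to fill in missing data". The rule at issue is "Variables with a missing rate above 20% will be excluded", and the same sentence goes on to place the outcomes in the imputation model. The only sensitivity analysis for missing data is complete case: "A complete case analysis will also be performed as a sensitivity analysis to assess the robustness of the results".

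Section 7.4 names the potential confounders for the comparison of PLWHIV with PrEP users. They include partner number and "smallpox vaccination history (yes vs no", and the set is fixed in advance for the first and second primary analyses. Section 7.5 repeats it with small variations and requires the interaction models to carry every listed adjuster. For the third primary analysis, 7.4 lists CD4 nadir, last CD4 count and other HIV characteristics as candidate predictors of severe mpox.

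Section 6.2 collects all items from routine records where they exist, and marks one of the confounders again: "Orthopoxvirus vaccination history (if available". Section 7.2 requires every primary and secondary endpoint to use the full analysis population. No expected missing rate is given for any variable.

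**The concern.** Whether a variable confounds the HIV comparison does not depend on how often it is recorded. Leaving out a confounder because it is 25% missing treats its effect as zero, when the observed 75% could inform an imputation that the plan already intends to run. Under 7.7 as written, record completeness across up to 12 sites could settle the content of the primary adjusted model after the data are in, overriding the choice made in 7.4.

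The variables at risk are not marginal. Vaccination history is the confounder that the protocol itself flags as possibly unavailable. The two partner adjusters (multiple partners yes/no, and number) appear to rest on a single item in 6.2, so they would probably be lost together. CD4 nadir is named in the primary objective, yet the list in 6.2 names the last CD4 count and not the nadir, so its completeness cannot be judged.

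**Working it through.** **1. The two readings of *excluded*.** The plan gives no figure here to reproduce, so the first step is to set the sections side by side.

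- *Excluded from the analysis.* The adjusted models in 7.4 and 7.5 lose a listed adjuster. This contradicts the fixed sets, and most directly the instruction in 7.5 that the interaction models contain all of them.
- *Excluded from the imputation model only.* The variable stays in the adjusted model but unimputed, so each completed data set loses every patient lacking it. Just above the threshold, fewer than 2000 × 0.80 = 1600 patients remain; at an assumed 35% missing, 2000 × 0.65 = 1300. This contradicts 7.2.

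The complete-case analysis does not settle the matter, because 7.7 does not say whether it would bring an excluded variable back. If it did, two variables each 25% missing independently would leave 2000 × 0.75² = 1125 patients.

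**2. Bias from dropping vaccination.** Inputs from the documents: about 2000 patients (Section 4), and 41% with HIV in the early report cited in Section 1, giving 820 vs 1180. Assumed: 12% risk in the unvaccinated (close to the 13% hospitalised in that report), a true HIV odds ratio (OR) of 1.0, and the vaccination rates and effects below.

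With unvaccinated risk r and vaccine odds ratio V, the vaccinated risk is rv = odds/(1 + odds), where odds = V·r/(1 − r). The risk in a group with a proportion p vaccinated is (1 − p)·r + p·rv.

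Worked case, V = 0.5, 25% vs 45% vaccinated: rv = 0.0638. PLWHIV: 0.75 × 0.12 + 0.25 × 0.0638 = 0.1060. PrEP users: 0.55 × 0.12 + 0.45 × 0.0638 = 0.0947. OR without vaccination = (0.1060/0.8940)/(0.0947/0.9053) = 1.13.

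| Vaccinated, PLWHIV vs PrEP | V | OR with vaccination dropped (truth 1.0) |
|---|---|---|
| 30% vs 30% | 0.5 | 1.00 |
| 25% vs 35% | 0.5 | 1.06 |
| 25% vs 45% | 0.5 | 1.13 |
| 25% vs 45% | 0.3 | 1.21 |
| 20% vs 50% | 0.3 | 1.34 |
| 35% vs 25% | 0.5 | 0.94 |
| 40% vs 20% | 0.3 | 0.83 |

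**3. False-positive rate.** For the four rows from 1.06 to 1.34, simulation (500 data sets each) gave type I error of 8%, 12%, 23% and 48%. The dashboard in 6.1 reports 53/907 = 5.8% hospitalised. At that risk the ORs barely move, but with fewer events the normal approximation (z = ln OR / SE from the two-by-two table) gives about 6%, 9%, 14% and 25%.

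**4. Imputing instead of dropping.** Simulation with n = 2000, equal groups, 13% risk in PrEP users, a true OR of 1.5, 10 imputations, 300 replicates, and missingness depending on HIV status and outcome:

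| Vaccinated; V; missing | Dropped: OR (coverage) | Imputed: OR (coverage) |
|---|---|---|
| 20% vs 40%; 0.5; 30% | 1.69 (84%) | 1.50 (96%) |
| 10% vs 40%; 0.3; 30% | 1.98 (34%) | 1.51 (95%) |
| 20% vs 40%; 0.5; 40% | 1.70 (86%) | 1.51 (94%) |

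**5. If data are not missing at random.** Suppose vaccination status is missing for 45% of the unvaccinated and 15% of the vaccinated. Among those recorded, the odds of being vaccinated are then multiplied by 0.85/0.55 = 1.55 in every HIV-by-outcome cell. Imputing from those odds turns a true OR of 1.0 into 0.99, 0.98, 0.96 and 0.95 for the four rows in step 3. For the last of these, the odds of the outcome in the unvaccinated become 0.0922/0.6303 = 0.1463 in PLWHIV and 0.0529/0.3425 = 0.1544 in PrEP users, a ratio of 0.95.

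**The case against.** The strongest defence is that the sentence in 7.7 goes on to speak of the imputation model, so *excluded* may mean only that poorly recorded variables are not imputed, while 7.4 and 7.5 still govern the adjusted models. That reading is possible, and it is why this point does not assert that adjusters will be dropped. It does not rescue the rule, because the loss of patients in step 1 then follows.

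Several further objections stand, and they limit what can be claimed:

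- A reader might infer that the rule *would* remove vaccination and partner number. No missing rate is given, so removal is possible and not established. Partner number carries only the general availability caveat, and last CD4 has no special flag in a population described as under regular follow-up.
- A reader might infer that the adjusted HIV odds ratios will be confounded. That also needs vaccination to differ between the groups and to affect severity among people already infected. Section 1 speaks of protection against infection and says clinical evidence on the vaccine campaign is lacking.
- A reader might infer that the rule also removes time to lesion resolution, recorded as "Time to resolution of lesions, if known". The documents do not support this: the same sentence keeps outcomes in the imputation model, and 7.4 treats unknown resolution as right-censored.
- Imputation removes the bias only if data are missing at random, as step 5 shows.
- Ten imputations are adequate: relative efficiency is 1/(1 + 0.4/10) = 0.96 with 40% missing information.

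**Conclusion.** The point holds as a conflict within the plan and a risk to the primary comparison. Section 7.7 has no exemption for named exposures and adjusters, and either reading of the exclusion contradicts another section.

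The size cannot be fixed from the documents. On the stated assumptions, dropping vaccination moves a true HIV odds ratio of 1.0 to somewhere between 0.83 and 1.34. There is no bias if vaccination is equal in the two groups, and the direction depends on which group is more vaccinated. Under missing at random, imputation recovers the true value; under the one not-at-random pattern tried, it leaves a smaller error. The plan should be changed, but nothing here shows that the adjusted results will be wrong.

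**What to change.** - State in 7.7 what *excluded* means, and remove the 20% exclusion for every exposure and adjuster named in 7.4 and 7.5.
- Keep those variables in both the imputation and the analysis models whatever their missing rate, with outcome, HIV status, site and diagnosis date among the predictors in the imputation model.
- Report missingness for each of them separately in PLWHIV and PrEP users.
- For any of them above 20% missing, show the adjusted result with and without the variable, and add a delta-adjusted sensitivity analysis for data missing not at random. The with/without comparison alone does not test the missing-at-random assumption.
- Say whether the complete-case analysis uses the full adjustment set.

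More than ten imputations is optional. The cost is SAP wording, some computing time and slightly more analysis work, since chained-equation imputation is already planned. The drawback is heavier reliance on missing at random for poorly recorded variables, which the delta-adjusted analysis makes visible.
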